**Phase B) Pilot RCT**

Inclusion criteria: lactating women of at least 18 years of age and their exclusively breastfed infants within 30 days of delivery with informed consent. Children 6-59 months who are orally feeding with caregiver informed consent.

Exclusion criteria: regular maternal consumption of moringa in the month prior to study enrollment, receipt and consumption of food supplementation program, or inability to feed orally; for infant, significant congenital disease, inability to feed orally. For child: inability to feed orally or refusal to eat porridge (>3 days consecutively).

We anticipate enrolling up to 50 mother-infant dyads in each of two arms and 50 children in each of two arms.

We propose starting enrollment as soon as all ethical approvals obtained, personnel hired, and study supplies obtained; there is no additional sample composition of subjects. This study targets women and infants as breastfeeding infants have the potential to receive the greatest benefit from moringa leaf supplementation to their lactating mothers.

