increase breastmilk volumes thus increasing infant growth and may lead to improved intestinal health leading to increased absorption of nutrients consumed. Thus, we estimate a change from estimated 25% stunting prevalence to 6.5% stunting; in comparison, this is still double the prevalence of stunting in children under five years in the United States (3.5% UNICEF data 2016). At 80% power, this would require a sample size of 82 infants in each arm. Due to concern for loss to follow up and a possibility of a smaller effect than estimated, we aim to recruit 100 infants in each arm if external funding is obtained. That is 200 infants. We also estimate 50 children 6-59 months in each arm, that is 100 children. We also estimate 10-20 children trying moringa and placebo for the acceptability study. That is a total of 320 children.

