### We will implement:

A) a short acceptability study of acceptability, adherence, and preference for moringa dried leaf consumption and placebo consumption in porridge. Selection will be from lactating women 18 years and over and children 6-59 months; subjects will come from our target region of Kisumu.

B) a pilot placebo-controlled RCT of mother-infant dyads and their children 6-59 months who present for first postnatal check to two high volume rural maternal and child health centers in Kisumu, Kenya.

Inclusion criteria: lactating women of at least 18 years of age and their exclusively breastfed infants within 30 days of delivery with informed consent. Children 6-59 months of age who are eating food.

Exclusion criteria: regular maternal consumption of moringa, receipt and consumption of food supplementation program, or inability to feed orally; for infant, significant congenital disease, inability to feed orally. For mother or child: inability to orally feed or complete refusal (>3 days) to eat moringa or placebo porridge.

Sample size: 100 infant-mother pairs in each arm (n=400 participants total). 100 children in each arm (n=200)

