**Aim 3: Assess mechanisms of improved infant or child growth and nutritional status as defined by improved infant intestinal health using biomarkers of Environmental Enteric Dysfunction and prevalence of diarrhea**

Sample collection: Baseline and exit visit collection of stool samples, prevalence of diarrhea

Intestinal health measurements: Markers of environmental enteric dysfunction (fecal neopterin, myeloperoxidase, alpha-1- antitrypsin), and prevalence of maternal and infant acute diarrheal illness (>3 watery stools in 24 hours). The rationale for this choice of biomarkers comes from the largest study of markers of environmental enteric dysfunction to date, the MAL-ED cohort, that determined that fecal neopterin, myeloperoxidase, and alpha-1-antitrypsin provide the most sensitive measures of intestinal inflammation and integrity in breastfeeding infants.(50,51) MAL-ED additionally established improved performance of these fecal markers over the previous standard of urine lactulose:mannitol ratio to assess intestinal integrity. These assays will be completed at the UK Biomarker Analysis Laboratory with send-out as needed to UK approved facilities. The impact on intestinal health may also be visible in mothers directly consuming moringa. For this reason, we are collecting maternal stool and analyzing it for the same markers of EED as well as for fecal calprotectin as a measure of intestinal inflammation. In addition to more directly quantifying moringa's impact on intestinal health, increased maternal intestinal integrity may lead to improved nutrition and impact her breastmilk quality or quantity.

**Aim 3: Assess mechanisms of improved infant growth and nutritional status of infants as defined by improved breastmilk volume and composition including Vitamin A precursors and antioxidants.**

Sample collection: At exit, maternal breastmilk.

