## Statistical Analysis Plan – 58219

Statistical Analysis: Data analyses were performed using SPSS v28 (IBM Corp. 2021) with graphing via SPSS and Prism GraphPad (v9.5.1). Using an intention-to-treat approach, we performed univariate and multivariable analysis for primary and secondary outcomes as change from baseline per individual/group and between groups. We used Pearson's (for normally distributed data) or Spearman's (for non-normally distributed data) correlation to examine relationships between continuous variables, Pearson's chi square and Fisher's exact tests between categorical variables, and independent t-test or Mann-Whitney U test between binary and continuous variables as appropriate. Paired samples t-tests or Wilcoxon matched-paired sign-rank test were used for paired data. Continuous variables are presented here as mean with standard deviation (if normally distributed) as mean  $\pm$  SD or median with interquartile range (if not normally distributed) as median, IQR, while categorical variables are presented with counts and percentages. An alpha-level of 0.05 was used to determine significance. All enrolled participants who continued study activities through at least the first month were analyzed regardless of loss to follow up.

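### For the stool and blood markers the SAP fixes no measurement scale and names no between-arm estimate; a log-scale model adjusted for the enrolment value would give a ratio with a confidence interval and, if the markers are skewed, more power.

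*Combined protocol and SAP*

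**What the plan says.** The Statistical Analysis Plan commits to "univariate and multivariable analysis for primary and secondary outcomes as change from baseline per individual/group and between groups". For the comparison between arms it offers "independent t-test or Mann-Whitney U test between binary and continuous variables as appropriate". Normality is its stated criterion for choosing a correlation coefficient and for choosing mean with SD or median with IQR. For the between-arm test the criterion is left to judgement. "An alpha-level of 0.05 was used to determine significance" is the only decision rule, and sidedness is not given. The SAP names no transformation, no scale for any outcome, no normality test, and no between-arm estimate or confidence interval. A multivariable analysis is mentioned without model or covariates.

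The outcomes concerned are in Data Collection & Research Materials. Under Aim 3 they are "Markers of environmental enteric dysfunction (fecal neopterin, myeloperoxidase, alpha-1- antitrypsin") plus maternal fecal calprotectin. Under Aim 2, CRP is measured so that vitamin A can be assessed with and without correction for inflammation, and ferritin and soluble transferrin receptor are inputs to an index. The Study Design section has stool and capillary blood collected at enrolment and exit, so paired values exist.

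**The concern.** These markers are concentrations that cannot fall below zero, and such measurements are often right-skewed. For a participant whose exit value is r times the enrolment value x, the raw change is (r − 1)x and the log change is log r. Two participants with the same proportional fall therefore get different raw changes, ordered by where they started. Mann-Whitney limits the pull of outliers but does not remove this. Ranks of a single value survive a log transform; ranks of a difference do not.

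Two things are at stake. A proportional fall in gut inflammation, which is what Aim 3 looks for, may be detected less often than the same samples allow. And where Mann-Whitney is used, the plan leads to medians, IQRs and a p-value. For a pilot, a between-arm effect size with its uncertainty is a main product for planning later work.

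**Working it through.** **The plan's own figure.** The documents state no power for any marker. The only derived sample size is for stunting: "we estimate a change from estimated 25% stunting prevalence to 6.5% stunting" and "At 80% power, this would require a sample size of 82 infants in each arm". The usual formula, two-sided 0.05, is n = [1.96·√(2·p̄·q̄) + 0.8416·√(p₁q₁ + p₂q₂)]² / (p₁ − p₂)². With p₁ = 0.25, p₂ = 0.065 and p̄ = 0.1575 this is (1.0097 + 0.4194)² / 0.185² = 59.7, so 60 per arm (71 with continuity correction). The stated 82 is not reproduced. That is a separate matter and bears on nothing below.

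**Inputs from the documents.** Alpha is 0.05. Arm size is inconsistent: "We anticipate enrolling up to 50 mother-infant dyads in each of two arms and 50 children in each of two arms" against "Sample size: 100 infant-mother pairs in each arm (n=400 participants total"), while the application's maximum is 104 subjects. If all 104 were members of dyads, that is 104 / 2 / 2 = 26 dyads per arm. The calculations use 26, 45 (50 less an assumed 10% loss) and 50.

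**Inputs assumed.** Two-sided testing; log-normal values with log-SD s of 0.8 to 1.2 (0.5 as a milder case); enrolment-exit correlation ρ of the logs of 0.1 to 0.5; a multiplicative effect. The large effect is −0.6 log-SDs. At s = 0.8, 1.0 and 1.2 the ratio is exp(−0.48) = 0.62, exp(−0.60) = 0.55 and exp(−0.72) = 0.49, a fall of 38 to 51%.

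**Log-scale power by hand** (45 per arm, ρ = 0.3, large effect):
- Log change: standardised effect 0.6/√(2(1 − ρ)) = 0.6/1.183 = 0.507. Multiply by √(45/2) = 4.743 to get 2.405. Power ≈ Φ(2.405 − 1.96) = 67%.
- Log exit value adjusted for log enrolment value: 0.6/√(1 − ρ²) = 0.6/0.954 = 0.629. Times 4.743 is 2.983. Power ≈ Φ(1.02) = 85%.

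**Simulated power, same setting, s = 1.0.** Independent runs agree to within about 3 points.

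| Method | Marker falls | Marker rises |
|---|---|---|
| Raw change, t-test | 35–36% | – |
| Raw change, Mann-Whitney | 48–50% | 64–65% |
| Log change, t-test | 67–68% | 67% |
| Raw exit value, adjusted | 63–66% | 64% |
| Log exit value, adjusted | 84–85% | 84% |

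Selecting t-test or Mann-Whitney by a Shapiro-Wilk test (an assumed rule) gave 50% for the fall, the same as Mann-Whitney.

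**How the unadjusted gain (log change over Mann-Whitney or the data-driven choice) moves:**
- Large fall, 45 per arm, s 0.8–1.2, ρ 0.1–0.5: +15 to +21 points; about +11 at s = 0.5.
- Large fall, 26 per arm, s 0.8–1.2: +9 to +20.
- 50 per arm, ρ = 0.5, effect set so that log change has about 80% power: +16, +18 and +22 at s = 0.8, 1.0 and 1.2.
- Half the effect, s = 1.0, ρ = 0.3: 18% to 23% at 45 per arm (+5), about +3 at 26 per arm. Across settings, about +1 to +8.
- Rising marker: 0 to +4.

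The asymmetry has a simple cause. A fall shrinks exit values, so the raw difference is driven by the enrolment value, which carries no treatment effect. A rise stretches exit values, so the raw difference is driven by them. Adjusting for enrolment removes that asymmetry: in the table the adjusted log scale leads the adjusted raw scale by about 20 points in both directions.

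**Type I error** of the data-driven choice of test was 4.9% (50 per arm, s = 0.5 and 1.0).

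**The case against.** The strongest objection is to the power figures. Every biomarker input is assumed, 45 per arm appears nowhere in the documents, and log-normal data with a purely multiplicative effect is the case in which logs do best. No additive effect and no values below detection were simulated. All of that stands. A reader might infer that logs would recover a flat 15 to 20 points; the documents cannot support that, because the figure needs a strongly skewed marker, a large effect and a fall. Ferritin, which better iron status would be expected to raise, falls outside it.

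A reader might also infer that choosing the test after seeing the data inflates false positives. The check does not show this.

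Nor do the documents say outright that the change is on the raw scale. That is the natural reading of change from baseline with no transform named, but it rests on silence, and the outcome-measures attachment is not visible. It is also too strong to say that Mann-Whitney can give no effect size, since a Hodges-Lehmann shift can accompany it. The valid complaint is that the SAP names no between-arm estimate or interval. Finally, Aim 3 does not rest on these markers alone: it also uses diarrhea prevalence and breastmilk volume and composition.

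What survives is the unspecified scale and the missing estimate, neither of which depends on a simulation.

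**Conclusion.** The point holds as one of efficiency and interpretability, not validity. The SAP fixes no scale for zero-bounded markers and plans no between-arm estimate with a confidence interval. If the markers are right-skewed, which is plausible but not documented, a log scale is the better choice. Under log-normal data and a multiplicative effect with 26 to 50 per arm, the unadjusted gain is about 10 to 22 points for a large fall, a few points for half that effect, and about 0 to 4 points for a rise. Adjusting for the enrolment value on the log scale is the more dependable improvement, because it helps in both directions. In none of the settings simulated did the log scale lose power. Confidence is medium, because the size rests wholly on assumed SDs, correlations and effects.

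**What to change.** - For each fecal marker, and for CRP, ferritin and soluble transferrin receptor where they are analysed as outcomes in their own right, regress the log exit value on arm and log enrolment value, whatever a normality check shows. Report the between-arm ratio of geometric means with its 95% CI.
- State one rule per assay for values at zero or below detection: a named substitution, or a censored (Tobit) regression.
- Leave the transferrin receptor-ferritin index on its own defined scale.
- Keep Mann-Whitney as a sensitivity check.

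The SAP is written in the past tense. If the analyses are already done, the log-scale model should be presented openly as a re-analysis beside the results obtained under the present plan.

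The cost is a short SAP paragraph and a modest amount of analysis, with no new samples or visits. The downside is that readers get a ratio instead of a difference in assay units; geometric means by arm and visit alongside it would help.

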### Hypothesis and Aims:

Moringa leaf supplementation in porridge and placebo in porridge will be acceptable to lactating mothers and 6-59 month old children. Three months of high dose Moringa leaf supplementation to breastfeeding mothers of neonates in Kisumu, Kenya will lead to improved infant growth and nutrition compared to controls.

Aim 1: Determine acceptability, composition, and preference of consumption of moringa and placebo in porridge.

Aim 2: Test the hypothesis that three months of daily moringa leaf supplementation to breastfeeding mothers for infants and to children 6-59 months for themselves will improve childhood growth and nutritional status via measurements of growth, Vitamin A, and iron deficiency.

Aim 3: Assess mechanisms of improved infant and childhood growth and nutritional status as defined by 1) improved intestinal health using biomarkers of Environmental Enteric Dysfunction and prevalence of diarrhea, and 2) improved breastmilk volume and composition.

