Breastmilk measurements: Volume (24 hour pre and post-breastfeeding infant weights), vitamin A and its precursors (retinols), antioxidants (catalase, Vitamin E, lactoferrin), and nutritional profile (fatty acid profile and protein analysis). Measures of breastmilk volume include assessment of 24 hour breast pumping or hand expression or weighing the infant before and after feeding for 24 hours.(52–56). Breastmilk contains a wide variety of nutrients necessary for growth and multiple bioactive compounds that can dramatically affect infant health by modifying inflammation. Breastmilk components vary according to time from birth as well as maternal nutritional status, dietary intake, and disease states. Compounds that act to modify inflammation include vitamins and their precursors such as Vitamin A, retinols, and Vitamin E, as well as catalase, lactoferrin, and certain fatty acids.(57–59) All assays will be completed in Eurofin Laboratories. Due to the likelihood of moringa to improve any pre-existing maternal vitamin A or iron deficiency and this, in turn, affecting the composition of breastmilk (most notably in vitamin A precursors), we will also collect maternal blood for vitamin analysis.

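### The SAP names only unadjusted correlation for links between continuous variables and does not say whether its multivariable analysis covers Aim 3 marker-growth links; enrolment age or arm can then pass for a mechanism.

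*Combined protocol and SAP*

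**What the plan says.** Aim 3, under Hypothesis and Aims, is to "Assess mechanisms of improved infant and childhood growth and nutritional status as defined by" better intestinal health (fecal biomarkers and diarrhea) and better breastmilk volume and composition.

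The Statistical Analysis Plan – 58219 is one paragraph. It names Pearson's or, for data that are not normal, Spearman's "correlation to examine relationships between continuous variables". This stands in a list of bivariate tests chosen by variable type. No covariate, stratification by arm, partial correlation or mediation method is named. The same paragraph also says "we performed univariate and multivariable analysis for primary and secondary outcomes as change from baseline per individual/group and between groups", without naming a model or covariates, and "An alpha-level of 0.05 was used to determine significance".

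Three other places bear on the point:

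- Data Collection & Research Materials, in the breastmilk part of Aim 3: "Breastmilk components vary according to time from birth as well as maternal nutritional status", with diet and disease also listed.
- Phase B) Pilot RCT, inclusion criteria: "exclusively breastfed infants within 30 days of delivery".
- The justification of the number of children, in the Subject Children section: moringa is expected to raise milk volume and through it growth, possibly with better intestinal health. Stunting is planned to fall from 25% to 6.5%.

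**The concern.** Two variables that share a cause are correlated even when neither affects the other. The protocol itself supplies two candidate shared causes.

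- **Age at enrolment.** Follow-up is three months from a start anywhere in the first month of life, so the change in a milk marker depends partly on when the infant entered. If growth change does too, the two will correlate.
- **Arm.** If moringa raises milk volume and growth by separate routes, the two correlate across the combined arms without one acting through the other.

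At stake is how Aim 3 is read. A significant marker-growth correlation could be taken as evidence for a milk or gut pathway when it reflects age or arm. This is separate from the number of tests performed. The arm part also grows with the treatment effect, so it is largest in the situation where a mechanism would most naturally be claimed.

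**Working it through.** The plan gives no figure for its correlation analysis, so there is none to reproduce. Its only sample-size figure (82 infants per arm) is not used here.

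**Inputs from the documents.** Alpha is 0.05 (two-sided assumed). Enrolment age runs from 0 to 30 days. The stunting rates are 25% and 6.5%. Dyad numbers differ: 50 per arm in Phase B) Pilot RCT, 100 per arm in Study Design, and a maximum of 104 subjects in Project Information (about 52 dyads if all were dyads).

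**Assumptions.** There is no true marker-growth link. N is 90 or 100 dyads in equal arms. Age is uniform over the window. The shares of variance due to age, and the marker shifts, are assumed because the documents give none.

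**Step 1: growth shift implied by the stunting target.** For normal length-for-age Z scores with equal SD, the shift is z(0.935) − z(0.75) = 1.514 − 0.674 = 0.84 SD.

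**Step 2: correlation induced by a shared cause.**

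- Age only, explaining shares A and B of the two variances: r = √(A × B).
- Arm only, shifts d1 and d2 in within-arm SD: r = (d1·d2/4) / √[(1 + d1²/4)(1 + d2²/4)].

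For d1 = d2 = 0.5, r = 0.0625/1.0625 = 0.059. For 0.84 and 0.5, r = 0.105/√(1.1764 × 1.0625) = 0.094. For 0.84 and 0.84, r = 0.1764/1.1764 = 0.150.

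**Step 3: chance of p < 0.05.** By Fisher's z, with m = atanh(r)·√(N − 3), the chance is 1 − Φ(1.96 − m) + Φ(−1.96 − m). For example, r = 0.10 and N = 90 give m = 0.1003 × 9.327 = 0.936 and a chance of 15.5%.

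| Shared cause (no true link) | N | r | Unadjusted rejection |
|---|---|---|---|
| Arm 0.5 SD on both | 90 to 100 | 0.059 | 8.5% to 8.9% |
| Arm 0.84 SD growth, 0.5 SD marker | 100 | 0.094 | 15% |
| Arm 0.84 SD on both | 100 | 0.150 | 32% (33% simulated) |
| Age 20% of marker, 2% of growth | 90 | 0.063 | 9% |
| Age 20% of marker, 5% of growth | 90 | 0.100 | 16% |
| Age 10% of both | 90 | 0.100 | 16% |
| Age 20% of both | 90 | 0.200 | 47% (48% simulated) |

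Simulations agree within about 2 percentage points, and Spearman behaves like Pearson. If age and arm act on the marker only, the rate stays at about 5%.

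**Step 4: dependence on N.** With 200 dyads, the first three rows become 13%, 26% and 56%. With 52 dyads, the last two become 11% and 30%.

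**Step 5: after adjustment.** A partial correlation given arm and enrolment age rejects in 4.3% to 5.7% of simulated trials in every setting tried. This holds because age and arm are the only shared causes simulated. Suppose age explains 20% of each variable and another factor, such as maternal nutrition, 10% of each. The partial correlation is then 0.10/(1 − 0.20) = 0.125, and the adjusted test still rejects in about 21% to 22% of trials at N = 90.

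**The case against.** The strongest reply has five parts.

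- **The SAP lists multivariable analysis.** A reader might infer that correlation is the only tool available. The documents do not support that. Nor do they show that the multivariable analysis covers marker-growth links or adjusts for arm and age. What stands is a gap in specification.
- **The correlation clause is generic.** It is not tied to Aim 3 and does not say that the arms are combined. Both are inferences. They are reasonable, because no other method is named for a continuous marker against continuous growth.
- **Aim 3 can be read as change in the markers themselves.** The listed t-test or Mann-Whitney test compares those between arms, protected by randomisation. This is right, and the fix keeps it. The protection does not extend to correlating a marker with growth.
- **Growth is expressed as WHO Z scores.** These already standardise for age, which weakens the age route on the growth side. They may not remove it, because Z scores can themselves drift with age. Milk and fecal markers are not described as age-standardised.
- **Direction matters.** If age acts in opposite directions on the two variables, the false link is negative rather than positive. The test is still inflated, but not towards the hoped-for mechanism.

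**Conclusion.** The point holds in a conditional form. The SAP leaves marker-growth analysis at an unadjusted correlation unless its unspecified multivariable analysis is meant to cover it. Under that reading, false links are possible but not certain: age or arm must move both variables.

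With 90 to 100 dyads, the false-positive rate runs from about 9% (arm 0.5 SD on both, or a weak age effect on growth) to 33% for arm effects as large as the stunting target implies, and to 48% if age explains 20% of both variables. The lower figures are at least as plausible as the higher ones for age, given the Z scores. The 0.84 SD also assumes normality and that a shift in Z score carries over to the growth variable analysed.

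A reader might infer that spurious mechanisms will appear. The documents do not support this, because they give no size for any age effect or any marker effect. The child cohort (6 to 59 months) could face the same issue for gut markers, but it has no milk measure and is not sized here.

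**What to change.** For Aim 3 marker-growth associations, state in the SAP that the analysis is a partial correlation (on ranks if skewed), or a regression of growth on the marker, adjusted for arm and age at enrolment. State whether the multivariable analysis is meant to cover these links, and list its covariates.

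Report the results as associations, since other shared causes named in the protocol, such as maternal nutritional status, may remain. Rest any statement on what moringa does to milk or gut markers on the between-arm comparison that the SAP already allows.

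The cost is a few sentences of SAP text and two variables that the trial must already hold: arm, and age, which the Z scores require. No new data are needed. The SAP is written in the past tense; if the correlations have already been run, the adjusted analysis should be added and labelled as specified afterwards.

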### Data collection:

Monthly anthropometrics for mother, infant, and child. These include infant weight, length and maternal and child weight, height/length, and mid-upper arm circumference.

Enrollment and exit quantitative surveys including but not limited to Food Frequency Questionnaire from which we will calculate Dietary

Diversity Score.

Mother, infant and child finger or finger/ heel stick for hemoglobin and capillary blood collection at study enrollment and exit.

Mother, infant and child feces collection at study enrollment and exit.

Daily recording by parent in provided diary of daily moringa percent consumption, incidence of diarrhea, diagnosis by health professional of medical condition in mother, infant, or child.

Lactating Women:

24 hour volume of breastmilk at study enrollment and exit

Breastmilk sample collection (est. 5ml) at study enrollment and exit

We would like to complete one more anthropometric measurement (weight and length) of enrolled infants in the next few months; this is 8-12 months from study start.

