### Phase B)

Participants regularly receive postnatal appointments at their health center for routine child check with health center staff. During this visit, our trained study personnel will enroll the participants and separately perform anthropometrics (weight, height or length, mid upper-arm circumference), collect blood, fecal, and breastmilk sample, and distribute study supplies. At monthly visits (month 1, 2, exit visit at month 3), followup will occur at the participant's study site. At these visits, study staff will perform anthropometrics, review porridge and/or moringa consumed, review parental diary, distribute study supplies, and at end visit will again collect blood, fecal, and breastmilk samples as applicable. Compliance with porridge-moringa ratio will be assessed by review of parent recorded amount consumed in the diary and direct visualization of percentage of porridge and leaf powder remaining prior to distribution. This will occur via verbal recall for parents identifying as illiterate.

Biological samples of mothers, infants and children (blood by heel stick or finger stick and stool) will be collected by trained study personnel at the presenting health center on enrollment and exit (3 months). Hemoglobin will be assessed by Hemoccue® utilizing a capillary (heel or finger) stick with direct readout. Capillary blood by heel or finger stick will be transferred to special paper and dried appropriately to create Dried Blood Spots by a standardized process and/or stored in aliquot containers. Fecal collection will occur on the day of monthly presentation to the health center, or kits and instructions will be given to caregivers and the stool collected by study personnel in the participant's village. Hemoglobin will be recorded to the nearest 0.1 g/dL by Hemoccue®. Stool, breastmilk, and blood samples will be immediately chilled and transported to Kenya Medical Research Institute Lab (KEMRI) in Kisumu, processed, and stored at -80 degree C freezers until transport. Samples will then be shipped on dry ice to the University of Kentucky or to the contracted laboratory for analysis. Breastmilk will be transported to Eurofin Laboratories or the laboratory of analysis. Breastmilk volume will be performed at enrollment and exit by 24 hour breastmilk volume pumped by hand pump that we supply and measured with the milk subsequently fed to the infant.

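### Participants lost after month 1 are said to be analysed, but they have no change value for the exit-only outcomes and no stated way into the month-3 growth comparison

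*Combined protocol and SAP*

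**What the plan says.** The SAP (Statistical Analysis Plan – 58219) sets the form of the outcomes: "Using an intention-to-treat approach, we performed univariate and multivariable analysis for primary and secondary outcomes as change from baseline per individual/group and between groups". It defines the analysed set in its last sentence: "All enrolled participants who continued study activities through at least the first month were analyzed regardless of loss to follow up". For continuous outcomes between arms it names "independent t-test or Mann-Whitney U test between binary and continuous variables as appropriate". For repeated values it says: "Paired samples t-tests or Wilcoxon matched-paired sign-rank test were used for paired data". It names no imputation, no last-value rule, no repeated-measures model and no assumption about missing data. The multivariable analysis is mentioned without a model or covariates.

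The schedule is in the protocol. Research Procedures, Phase B, says: "At monthly visits (month 1, 2, exit visit at month 3), followup will occur at the participant's study site". For samples, staff "at end visit will again collect blood, fecal, and breastmilk samples as applicable". Study Design, Data collection, agrees: blood, stool, the milk sample and 24-hour milk volume are taken at enrolment and exit. Growth is different: "Monthly anthropometrics for mother, infant, and child". Diarrhea is entered daily in a diary that staff review at the monthly visits.

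**The concern.** A change from baseline needs a second value. A participant who passes month 1 and then leaves belongs to the SAP's analysed set but has no second blood, stool or milk value. Results for these outcomes would come from people who reached the exit visit, while the SAP's wording tells the reader that everyone past month 1 was included.

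For growth the same participant has one or two usable follow-up visits, and the SAP does not say what to do with them. A t-test or Mann-Whitney test takes one change per person. The analyst must drop the participant or let a shorter change stand beside 3-month changes. The two choices give different estimates and different numbers analysed, and nothing in the SAP settles which was used.

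**Working it through.** **Inputs.** Visits at enrolment and months 1, 2 and 3 (Research Procedures, Phase B). Sample timing (same section, and Study Design, Data collection). Up to 50 dyads and 50 children per arm (Study Population, Phase B); Study Design gives 100 per arm, so both are shown.

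**No documented loss rate.** The justification of numbers in the children's section states 82 infants per arm at 80% power for stunting of 25% against 6.5%, and a target of 100 if external funding is obtained. It attributes the margin to loss and to a possibly smaller effect, without a split, so the margin is not a loss rate. The 82 also does not reproduce. With two-sided alpha 0.05 (sidedness assumed), n = [1.96·√(2·0.1575·0.8425) + 0.842·√(0.25·0.75 + 0.065·0.935)]² / 0.185² gives 60, or 71 with continuity correction. Nothing below uses it; loss is assumed at 10%, 20% and 30%.

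**Step 1: what each outcome has.**

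| Outcome | Enrolment | Month 1 | Month 2 | Month 3 |
|---|---|---|---|---|
| Weight, length/height, arm circumference | yes | yes | yes | yes |
| Hemoglobin, retinol binding protein, ferritin/transferrin receptor | yes | no | no | yes |
| Fecal markers of enteric dysfunction | yes | no | no | yes |
| Milk volume and composition | yes | no | no | yes |
| Diarrhea | daily diary throughout | | | |

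A participant lost after month 1 has one follow-up growth value and none for rows 2 to 4. One lost after month 2 has two growth values and still none for rows 2 to 4.

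The milk row has a side issue: Data Collection & Research Materials lists the milk sample under Aim 3 at exit only. If that governed, nobody would have a change in milk composition. These sections need reconciling.

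**Step 2: participants with a change value, exit-only outcomes.** Number per arm = n(1 − d), where d is the share lost before exit.

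| d | from 50 | from 100 |
|---|---|---|
| 10% | 45 | 90 |
| 20% | 40 | 80 |
| 30% | 35 | 70 |

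**Step 3: growth, if the last available change were used.** Assume half the loss falls after month 1 and half after month 2, and that the effect grows linearly over three months. The estimate as a share of the true month-3 effect is (1 − d) + (d/2)(1/3) + (d/2)(2/3) = 1 − d/2. That gives 95%, 90% and 85% at 10%, 20% and 30% loss.

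**Step 4: growth, if leavers were dropped.** Assume within-person correlation of 0.7 to 0.9, ignorable dropout, the same split of loss and a common enrolment mean. A likelihood-based repeated-measures model keeps 92–94% of full information on the month-3 difference at 10% loss, against 90% for a baseline-adjusted analysis of completers. At 20% loss it keeps 84–88%, against 80%.

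**The case against.** The strongest reply is that the SAP's sentence only says who belongs to the analysis set, each person contributing whatever outcomes they have. On that reading it makes no promise of an exit sample from everyone. The reading is fair, but it concedes the point: the set behind each exit-only result is then the people with an exit sample, which the SAP does not say, and the month-3 growth question stays open.

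Second, the SAP mentions multivariable analysis, which might have used the monthly data. It might, so a reader should not infer that those data were certainly discarded or mixed. The documents show only that the named tests cannot use them properly and that no other model is described.

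Third, the protocol provides reminders and home visits for missed visits (Data Collection & Research Materials, Quality Control). These reduce loss and could recover exit measurements, so it would be wrong to say follow-up is neglected. They give no analysis rule for those still lost. One sentence ties stool collection to the monthly presentation, but the same section limits stool to enrolment and exit, so it reads as logistics. The further infant measurement at 8–12 months is weight and length only and cannot stand in for a month-3 value.

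Fourth, the precision gained from a mixed model is modest for a pilot. That stands. The main gain is that every growth value is used at its correct time.

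**Conclusion.** The concern holds in a limited form. As written, the rule cannot be carried out for hemoglobin, the vitamin A and iron markers, the fecal markers or the milk outcomes, because participants lost after month 1 or 2 have no change value and no imputation is planned. For growth, the treatment of these participants in the month-3 comparison is undefined under the named tests. This should be corrected but is not fatal to a pilot.

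The size is unknown because no loss rate is given. The figures of 45 to 35 of 50 per arm, and 95% to 85% of the month-3 growth effect, are illustrations. The second set rests on a last-value rule the SAP does not state, on linear build-up and on an even split of loss.

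Three stronger readings are tempting and not supported. One is that every Aim 3 outcome fails: diarrhea is recorded daily and is not affected. Another is that the gap between 82 and 100 documents 18% loss. The third is that bias must run toward no effect: that needs an effect that accumulates, and dropout that differs by arm could push either way.

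**What to change.** - **Z-scores and arm circumference:** use a repeated-measures mixed model on enrolment and months 1, 2 and 3 with arm, visit and arm-by-visit, and report the month-3 arm contrast. State the assumption that dropout is ignorable given the observed data.
- **Stunting at 3 months:** compare arms among participants with a month-3 length and report that number per arm.
- **Blood, stool and milk outcomes:** replace the clause on loss to follow-up with an analysis set of participants who have an exit sample, and report the number per arm for each outcome.

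The SAP is written in the past tense, so the analysis may already be done. The change needs only revised wording and one standard model on data already collected. The price is smaller stated numbers for the exit-only outcomes.
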